7.0 Protocol Treatment

7.1 Treatment Schedule

Arm	Agent	Dose Level	Route	Day
A	lenalidomide	2.5 mg	Oral	1-14
	lenalidomide	5 mg*	Oral	15-42
	Aspirin	325 mg	Oral	1-42
	Plevnar 13®**	1 dose	IM	15
B	Plevnar 13®**	1 dose	IM	15

* Unless dose reduced for adverse events, see Section 8.0

** Plevnar 13® vaccination should be administered on day 15 regardless of lenalidomide toxicity unless treating physician determines it should be held. If Plevnar 13® held, it should be administered as soon as deemed appropriate by treating physician.

7.2 For this protocol, the patient must return to the consenting institution for evaluation on Day 15 (+/-3 days) and Day 43 (+/-4 days) of the study.

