8.0 Dosage Modification Based on Adverse Events

Strictly follow the modifications in this table. If multiple adverse events are seen, administer dose based on greatest reduction required for any single adverse event observed.

ALERT: *ADR reporting may be required for some adverse events (See Section 10)*

8.1 ARM A: Dose Levels (Based on Adverse Events in Tables 8.2).

Dose Level	Lenalidomide Days 1-14	Lenalidomide Days 15-42
0	2.5 mg p.o. once daily	5 mg p.o once daily
-1	2.5 mg p.o. every other day	2.5 mg p.o. once daily
-2	2.5 mg p.o. Mondays and Thursdays	2.5 mg p.o. every other day

* Dose level 0 refers to the starting dose.

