13.0 Treatment/Follow-up Decision at Evaluation of Patient

NOTE: As of Addendum 4, Event monitoring will no longer be required

- 13.1 After completion of the Day 43 response to vaccine evaluation, patients will discontinue treatment and enter one cycle of OBSERVATION (28 days after end of first cycle +/- 10 days) and then enter EVENT MONITORING.
- 13.2 If Lenalidomide is discontinued due to patient refusal or noncompliance, unacceptable toxicity, or intercurrent illness that makes treatment assessment difficult and the patient received the Prevnar 13 vaccine, they will receive their Day 43 response to vaccine evaluation at which point they will then enter one cycle of OBSERVATION (28 days after end of first cycle +/- 10 days) and then enter EVENT MONITORING.
- 13.3 If a patient on Arm A does not receive the Prevnar 13 vaccine, they will discontinue treatment and go directly to event monitoring per Section 18.0 of the protocol. If a patient on Arm B does not receive the Prevnar 13 vaccine, they will be deemed a cancel and will be removed from the study per Section 13.6 of the protocol.
- 13.4 A patient is deemed *ineligible* if after registration, it is determined that at the time of registration, the patient did not satisfy each and every eligibility criteria for study entry.
 - If the patient received treatment, the patient will go directly to event monitoring. All data up until the point of confirmation of ineligibility must be submitted. Event monitoring will be required per Section 18.0 of the protocol.
 - If the patient never received treatment, on-study material and the End of Active Treatment/Cancel Notification Form must be submitted. No further data submission is necessary.

Note: Due to the nature of the disease, if the patient is diagnosed with DLBCL within the first cycle of treatment, it will be assumed that the DLBCL was present at registration. The patient will be deemed ineligible per Sec 3.29c.
- 13.5 A patient is deemed a *major violation*, if protocol requirements regarding Lenalidomide treatment during Days 1-42 are severely violated such that evaluability for primary end point is questionable. All data up until the point of confirmation of a major violation

must be submitted. The patient will go directly to the event-monitoring phase of the study. Event monitoring will be required per Section 18.0 of the protocol.

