We plan to send serum specimens to the Bacterial Respiratory Pathogen Reference Laboratory at University of Alabama Birmingham for pneumococcal opsonophagocytic assays. This laboratory is directed by [name], Professor of Pathology. Samples will be stored at Mayo until batch shipped to UAB.

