16.0 Statistical Considerations and Methodology

16.1 Overview:

This is a randomized Phase II study designed to compare the response rate of the control arm (Pevnar 13 alone) to the experimental arm (Pevnar 13 plus lenalidomide).

16.11 Primary Endpoint:

The primary endpoint of this trial is the rate of response to the Pevnar 13 vaccine, which will be compared between the two arms. A response will be defined as a four-fold rise from pre-vaccine (day 15) to 28 days after immunization (day 43) for ≥ 2 of the 3 serotypes studied by opsonophagocytic activity (OPA) of antibodies from sera. Throughout Section 16.0, response will be considered synonymous with “success”, unless specified otherwise. All patients meeting the eligibility criteria who have signed a consent form and, received the Pevnar 13 vaccine will be evaluable for response, with the exception of patients who are determined to be a major treatment violation or flag.

16.2 Statistical Design:

16.21 Decision Rule:

It has been shown that CLL patients have poor response to vaccines. In previous studies, responses to the polysaccharide pneumococcal vaccine (Pneumovax) have been remarkably low, with responses ranging from 10-22%.^{13,14} Similar responses are expected with the Pevnar 13 vaccine. The addition of lenalidomide is expected to increase response rates to Pevnar 13 vaccine.

A randomized trial comparing the experimental arm (Pevnar 13 plus lenalidomide) against the control arm (Pevnar 13 alone) will be conducted as described by Rubinstein³⁴. We will enter 26 evaluable patients on each arm of the study using a 1:1 randomization scheme utilizing the Pocock and Simon dynamic allocation procedure³⁵, where patients are stratified based on age (<65 vs. ≥ 65), Rai stage (MBL or 0 vs. I), and previous Pneumovax (yes vs. no). A sample size of 26 patients per arm provides 80% power to detect an improvement in response rate from 10% to 30%, using a one-sided test at a significance level of 0.16 (EAST 6.2).

The z-score will be calculated for testing the null hypothesis that the difference of response rates between the two arms is equal to zero, based on the normal approximation with pooled variance of standardized test statistics.

16.211 Final Decision Rule: The final analysis will take place after all 52 evaluable patients have completed the response evaluation at 43 days.

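### The major-violation exclusion from the primary analysis can in practice remove only Arm A patients, even when they are eligible and vaccinated

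*Combined protocol and SAP*

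**What the plan says.** - **Definition.** Section 13.5 is the only definition of a major violation in the document: "protocol requirements regarding Lenalidomide treatment during Days 1-42 are severely violated such that evaluability for primary end point is questionable". It sets no threshold for severity and has no Arm B counterpart.
- **Treatment.** Under 6.22 and 7.1, Arm A receives lenalidomide plus vaccine, and Arm B receives vaccine alone without placebo.
- **Primary population.** Sections 16.11 and 16.311 make eligible, consented, vaccinated patients evaluable, "with the exception of patients who are determined to be a major treatment violation" or who took lenalidomide but missed the vaccine (13.7). Section 16.312 divides successes by evaluable patients.
- **Missing titres.** Under 16.311, an evaluable patient in either arm without both OPA titres stays in as a non-responder.
- **Follow-up.** Section 13.2 begins "If Lenalidomide is discontinued due to patient refusal or noncompliance, unacceptable toxicity, or intercurrent illness" and keeps the Day 43 evaluation for vaccinated patients. Section 13.5 asks for data only up to confirmation of the violation and continues: "The patient will go directly to the event-monitoring phase of the study". A note at the head of Section 13.0 adds: "As of Addendum 4, Event monitoring will no longer be required".
- **Schedule.** Sections 7.2 and 14.1 provide for the Day 43 visit and serum for all patients.
- **Numbers.** Sections 16.21 and 16.211 fix the decision at 26 evaluable patients per arm. Section 16.22 adds three per arm for ineligibility, cancellation, major treatment violation and missed vaccine together.

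**The concern.** This is an exclusion made after randomisation, in an open-label trial, on a judgement that can be applied to one arm only. Patients missing the vaccine are outside the evaluable set by definition, and ineligibility can arise in either arm. The major-violation exception is therefore the one rule that removes an eligible, vaccinated patient, and there is no comparable way for such a patient to leave Arm B. If patients who take lenalidomide badly differ in their capacity to respond to a vaccine, the two evaluable groups are no longer the groups that were randomised.

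The plan is also uneven. A vaccinated patient with no titre counts as a non-responder, while a vaccinated Arm A violator with valid titres can be removed. The sera go to an outside laboratory in batches ("Samples will be stored at Mayo until batch shipped to UAB"), which makes early knowledge of titres less likely. Nothing, however, requires violations to be classified before results are known.

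**Working it through.** **1. The plan's own figure.** Inputs from 16.21: 26 per arm, 10% vs 30%, one-sided 0.16, pooled z. The pooled standard error is √(2 × 0.20 × 0.80 / 26) = 0.1109. The unpooled one is √((0.10 × 0.90 + 0.30 × 0.70) / 26) = 0.1074. Power = Φ((0.20 − 0.994 × 0.1109) / 0.1074) = 0.798, against 80% stated. The cut-off z = 0.988 in 16.211 corresponds to p = 0.1616. The design figures reproduce.

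**2. Effect of a one-arm exclusion on a false positive decision.** Assume no drug effect and an overall response rate p in both arms. Of 26 + k vaccinated Arm A patients, k violators with response rate q are excluded and replaced, leaving 26 evaluable. The evaluable Arm A rate is then

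pA = ((26 + k)p − kq) / 26.

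For example, with p = 0.10 and k = 3, pA = 2.9/26 = 0.1115 if q = 0, and (2.9 − 0.6)/26 = 0.0885 if q = 0.20. The chance that z exceeds 0.988 is summed exactly over Bin(26, pA) against Bin(26, p). The rates p = 10% and 22% are the ends of the range quoted in 16.21. The documents give neither k nor q; k = 1 to 3 is assumed from the allowance in 16.22.

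| Violators excluded | Never respond (10% / 22%) | Respond like the others | Respond at twice the rate |
|---|---|---|---|
| 1 | 0.203 / 0.186 | 0.192 / 0.168 | 0.181 / 0.151 |
| 2 | 0.214 / 0.205 | 0.192 / 0.168 | 0.171 / 0.135 |
| 3 | 0.226 / 0.224 | 0.192 / 0.168 | 0.160 / 0.120 |

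The middle column exceeds 0.16 because of the normal approximation, not because of the exclusion.

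**3. One patient can change the decision at the fixed 26 per arm.** Let Arm B have 4/26.
- Non-responding violator kept, Arm A 6/26: pooled rate 10/52, difference 0.0769, standard error 0.1093, z = 0.704 (below 0.988).
- Violator replaced by a responder, Arm A 7/26: pooled rate 11/52, difference 0.1154, standard error 0.1133, z = 1.019 (above 0.988).

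The change depends on the replacement responding. If the replacement does not respond, the result stays at 6/26.

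**4. Power if all eligible vaccinated patients are analysed.** Arm A is Bin(26 − k, 0.30) plus Bin(k, q), over 26, against Bin(26, 0.10), computed exactly:

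| k | Violators respond at 10% | Violators never respond |
|---|---|---|
| 0 | 0.821 | 0.821 |
| 1 | 0.806 | 0.798 |
| 2 | 0.789 | 0.772 |
| 3 | 0.771 | 0.744 |

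**The case against.** **The affected group is small.** Section 13.2 keeps vaccinated patients who stop lenalidomide for refusal, noncompliance, toxicity or illness on the Day 43 path, and nothing in 16.311 excludes them for stopping. A reader might infer that every Arm A patient who stops lenalidomide is dropped; the text does not say that. Dose changes for adverse events are themselves protocol requirements ("Strictly follow the modifications in this table"), so following them would not naturally count as a violation, although no section says so outright. This narrows the problem without closing it: for refusal and noncompliance, nothing marks where 13.2 ends and 13.5 begins.

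**The population is prespecified, and this is a screening trial.** Section 16.22 budgets openly for violations, and under 16.211 a positive result only supports further testing. That lowers the stakes. But the trial randomises, stratifies and makes a formal between-arm decision, and prespecifying a one-arm exclusion does not make the remaining groups comparable.

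**The shift is modest.** One excluded non-responder adds 0.011 at 10% and 0.018 at 22%. The former is smaller than the excess of about 0.03 over 0.16 that the normal approximation already causes. The largest values need the whole allowance to be violators who never respond. This stands, and it limits the weight of the point.

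**Day 43 collection.** A reader might infer that 13.5 cancels the Day 43 visit. It does not say so, and 7.2 and 14.1 schedule the visit and serum for all. Equally, 13.5 lacks the explicit retention found in 13.2 and can be read as ending collection at confirmation. The objection that retaining the draw may not be free therefore stands.

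**Conclusion.** The point holds as a possible one-arm bias from a post-randomisation exclusion. The stronger inference, that the rule favours lenalidomide, is not supported: the documents give no violation count and no link between compliance and vaccine response. The table in step 2 moves in both directions, and the effect is nil if violators respond like the others. Nor does the point show an error in the stated sample size or power, which reproduce.

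Under the assumed counts of one to three, the exact false-positive probability ranges from 0.160 to 0.226 at a 10% response rate, around 0.192 with no selective effect. At 22% it ranges from 0.120 to 0.224, around 0.168. The reading assumes that the major treatment violation in 16.11 and 16.311 is the category defined in 13.5, and sets aside an Arm B patient who takes lenalidomide off protocol. The change should be made because it protects the randomised comparison at low cost; confidence in its practical size is moderate at best.

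**What to change.** Make one linked change.

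1. In 16.11 and 16.311, delete the major-treatment-violation exception, so that all eligible vaccinated patients are analysed in their assigned arm. Keep the violation-excluded set as a sensitivity analysis, with violations classified before OPA results are known.
2. In 13.5, state that vaccinated major violators keep the Day 43 evaluation and serum draw. Without this, step 1 would let 16.311 score them as non-responders for want of a titre, a penalty on Arm A only.
3. Reconcile 13.2 and 13.5 on refusal and noncompliance.

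The cost is wording and one sensitivity table. The Day 43 visit and draw are already in the schedule, but a patient classified before Day 43 may have a visit and draw that the present 13.5 could be read as skipping. The primary question becomes the effect of lenalidomide as assigned; the sensitivity analysis keeps the view without major violators. The power cost is that in step 4: with three violators, exact power is 0.771 if they respond at the control rate and 0.744 if they never respond, against 0.821 with none.

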14.0 Body Fluid Biospecimens

- 14.1 The collection of blood/blood products is **mandatory** for the translational/pharmacologic research component of this study.
Summary Table of Research Blood and Body Fluid Specimens to be Collected for this Protocol

Correlative Study (Section for more information)	Mandatory or Optional	Blood or Body Fluid being Collected	Type of Collection Tube (color of tube top)	Volume to collect per tube (# of tubes to be collected)	Baseline	Day 15 visit	Day 43 visit	Process at site? (Yes or No)	Temperature Conditions for Storage /Shipping
T cell immune function (repertoire, synapse) and plasma cytokine profile (14.21)	Mandatory	Whole Blood	Sodium heparin (green)	10 mL (5)	X	X	X	No	Refrigerate/ Cold pack.
Specific immune response to Pevnar 13 vaccination (Streptococcus pneumoniae IgG antibodies,, OPA)(14.22)	Mandatory	Serum	(red top)	10 mL (2)	X	X	X	No	Refrigerate/ Cold pack.

14.2 Background and Methodology

14.21 Global immune changes in CLL T cell function.

- a) *T cell repertoire*: T lymphocytes recognize complexes of major histocompatibility complex gene products and bound, processed peptides through T cell receptors (TcRs) that are heteroduplexes of alpha and beta subunits. T lymphocyte populations are characterized by diverse TcR repertoires that have been hypothesized to be essential for effective T lymphocyte responses to large numbers of pathogens. The importance of diversity in T lymphocyte populations for maintenance of robust immune responses relevant to human health has driven the development of methods to quantitate TcR repertoire diversity. We have developed a novel method to analyze diversity of murine TcR beta transcripts²⁹ designated as the BV:BJ matrix method. This is based on amplification in real-time PCRs using 252 combinations of BV (beta variable) and BJ (beta-joining)-specific primer pairs that derive from 21 BV and 12 BJ genes. This method is able to reliably analyze TcR repertoire diversity in total populations of T lymphocytes. Our studies and others in CLL patients have shown significant deficits in repertoire along with individual T cell populations that have major expansions.

Processing: Peripheral blood mono-nuclear cells will be isolated by Ficoll-hypaque separation and frozen in liquid nitrogen. Malignant CD19⁺ CLL B-cells will be positively selected while CD3⁺ T-cells will be negatively selected using MACS cell isolation kits with an autoMACSTM Pro Separator (Miltenyi Biotec, Auburn, CA).

Total RNA will be extracted, and residual genomic DNA will be removed with an RNase-Free DNase Set (Qiagen) and used to assess T-cell repertoire. Extracted RNA levels from 10⁶ CD3⁺ T-cells will typically range anywhere from 2-4 µg.

Assessment of T-cell repertoire using a BV-BJ Matrix Method: In brief, this method is designed to generate a single estimate of repertoire diversity and increase the success of identifying and sequencing transcripts that are expressed by expanded T-cell clonotypes. Since BV and BJ genes belong to relatively closely related families, BV- and BJ-specific primers are rigorously selected to ensure specificity and comparable efficiency.^{29,30}

- b) *T regulatory cells*: In addition, a relative increase of circulating regulatory CD4⁺ T cells (T-regs) and their function has been observed in CLL, providing yet another explanation for increased infections and diminished responses to vaccinations.

Processing: T-cells isolated by magnetic bead sort (outlined above), will undergo immunophenotyping by flow cytometry.

- c) *T cell synapse*: In CLL leukemic B cells inhibit normal T lymphocytes through the impairment of the formation of the immunologic synapse in a

contact-dependent manner. Because of the leukemic nature of CLL, these inhibiting cell contacts can occur ubiquitously. The resulting state of cellular immunodeficiency offers a plausible explanation for the frequent infections and secondary cancers seen in CLL. We have just reported on the administration of a 6 month course of lenalidomide in CLL patients following chemoimmunotherapy (CIT) where we found enhanced T cell synapse levels for the responding patients.³¹

Processing: T-cell: APC immune synapse bioassays: The ability of CD3⁺ T-cells to interact (% conjugation) with APCs (baseline fluorescently labeled CLL cells pulsed with superantigen, sAg) and assemble signaling complexes to the immune synapse site will be visualized and quantified using combined multi-color high-resolution imaging flow cytometry (ImageStream) and confocal (Zeiss) Imagestream/Axiovision quantitative image analysis software will characterize and analyze the functional organization of T-cell synapses including the receptor layer (CD4, CD8, co-signaling molecules), the signaling layer and the cytoskeletal layer as previously described.^{32,33} Granzyme B⁺ will act as a biomarker for CTL lytic synapses. These data will then be exported for statistical analysis to generate mean values at each treatment time-point using the published approach.^{32,33}

[figure not shown]
14.22 *Specific immune response to Prevnar 13® vaccination:*

Immunity following pneumococcal disease is directed primarily against the capsular polysaccharide of the bacteria serotype involved. Antibody mediated killing of *Streptococcus pneumoniae* by phagocytes is an important mechanism of protection. The two most common serologic methods for quantifying and evaluating the function of antibodies induced by pneumococcal vaccination are IgG quantification by enzyme-linked immunosorbent assay (ELISA) and measurement of opsonophagocytic activity (OPA) of antibodies from sera of vaccinated individuals. The OPA assay is a functional antibody assay that is important for the evaluation of candidate vaccines and is a requirement for the licensure of new pneumococcal conjugate vaccine formulations. OPA reflects *in vivo* mechanisms of defense against pneumococcal infection. **The measurement of functional antibodies has been shown to better correlate with protection in infant populations and it is also likely to be a better indicator for elderly populations than the measurement of antibodies specific to the capsular polysaccharides by ELISA assay.**²⁷ While there is no defined correlate of protection for pneumococcal vaccines, it is thought that OPA titers are associated with protection against invasive pneumococcal disease. The primary endpoint for Prevnar 13® adult clinical trials that led to the FDA approval of Prevnar 13® relied on immunogenicity endpoints of OPA geometric mean ratio (GMT) and proportion achieving at least 4-fold increase in OPA titer.²⁸ Nevertheless, even when assessing OPA titers, most vaccine trials also measure and report quantitative IgG antibodies specific to *Streptococcus pneumoniae* serotypes.

- We will report pre-vaccination (baseline) and Day 28 post-vaccination OPA GMTs for each serotype (4, 9V, 23F) in vaccine group and vaccine group + lenalidomide.

- We will report pre-vaccination (baseline) and Day 28 post-vaccination *Streptococcus pneumoniae* serotype specific IgG GMTs for each serotype (1, 3, 4, 5, 6B, 7F, 9V, 14, 18C, 19F, 19A, and 23) in vaccine group and vaccine group + lenalidomide.
- Correlative endpoints for vaccine immunogenicity will include comparison of fold change in OPA GMT for each serotype (4, 9V, 23F) between vaccine group and vaccine + lenalidomide group and comparison of fold change in *Streptococcus pneumoniae* quantitative IgG level for each serotype (1, 3, 4, 5, 6B, 7F, 9V, 14, 18C, 19F, 19A, and 23) between vaccine group and vaccine + lenalidomide group.

We plan to send serum specimens to the Bacterial Respiratory Pathogen Reference Laboratory at University of Alabama Birmingham for pneumococcal opsonophagocytic assays. This laboratory is directed by [name], Professor of Pathology. Samples will be stored at Mayo until batch shipped to UAB.

14.3 Blood Products Handling

14.31 **Kits are required for this study for non-Mayo Rochester sites.**

The kit contains supplies and instructions for collecting, processing, and shipping specimens.

Participating institutions may obtain kits by e-mailing [REDACTED]. E-mail requests should include the site address, contact information and number of kits being requested.

Kits will be sent via FedEx® Ground at no additional cost to the participating institutions. **Allow 3 to 4 business days to receive the kits.**

14.32 Label specimen tubes with protocol number, patient initials (last name, first name), study patient ID number (if available) and date of collection.

14.33 Collect all peripheral blood according to specific kit instructions (see Appendix VI) and table above.

